9.1.5 Primary Safety Endpoint

This category includes the 8 pre-specified adverse events that will be analyzed as the Primary Safety Endpoint for the study:

- 1. Serious Adverse Event: any serious adverse event that:
 - Results in death,
 - Is life-threatening,
 - Requires hospitalization or prolongs existing hospitalization,
 - o Requires intervention to prevent permanent impairment or damage, or
 - \circ $\;$ Results in persistent or significant disability/incapacity.
- 2. Allergic Reaction: Type A, anaphylactoid or Type B dialyzer reactions to dialyzer, blood tubing or chemical disinfectant.
- 3. **Blood Loss**: blood loss resulting in hemodynamic compromise that leads to death, transfusion or fluid resuscitation with greater than 1 liter of crystalloid IV fluids.
- 4. **Hemolytic Reaction**: hemolytic reactions due to disinfectant exposure, dialysate temperature, mechanical failure or other device related causes.
- 5. Infection: any infection related to catheter, its tunnel or exit site, AV fistula, or AV graft.
- 6. Intra-Dialysis Event: a significant clinical event such as loss of consciousness, cardiac arrest, or seizure caused by device failure.
- 7. Vascular Access Complication: defined as AVF or AVG clotting during the dialysis procedure, bleeding for more than 30 minutes post-dialysis for 3 consecutive sessions, difficulty with vascular access resulting in inability to initiate or complete dialysis treatments or complications related to hemodialysis catheters (not including reduced blood flow in catheter or TPA or catheter exchange).
- 8. **Pyrogenic Reaction:** onset of objective chills (visible rigors) and fever (oral temperature greater than or equal to 37.5 degrees Celsius) in a Subject who was afebrile and who had no recorded signs or symptoms of infection before treatment.

9.2 Recording Adverse Events

9.2.1 Adverse Event Categorization

Reported Adverse Events will be categorized into one of the following two categories:

- 1. Primary Safety Endpoint: This category includes the 8 pre-specified adverse events that will be analyzed as the Primary Safety Endpoint for the study.
- 2. Other Adverse Events: This category includes all reported adverse events that meet the definition in Section 9.

The proposed categorization will serve to focus reporting, adjudicating, and analysis efforts to those categories most relevant for demonstrating the investigational device's relevant safety profile.

It is the intention of the Sponsor that AE's be collected in a uniform manner over the course of the study (independent of study arm) through the use of a Subject questionnaire. The Subject will be asked to complete a questionnaire regarding signs and symptoms experienced during each treatment. During regularly scheduled clinical follow-up visits during the trial, study staff will review the signs and symptoms noted by the Subject and provide education, as needed, on how they are documented. The study staff will determine whether subject reported signs and symptoms meet the definition of an AE as specified in Section 9. This approach attempts to eliminate any potential observed differences in AE rates between the study arms that are solely due to reporting sources or techniques.

Prior to analysis, all adverse events (AEs) will be coded using the Medical Dictionary for Regulatory Activities (MedDRA). Based on these coded terms, treatment emergent AEs will be summarized by treatment period, by severity, relation to procedure and relation to device.

9.2.2 Other Adverse Events

The Investigator will monitor the occurrence of adverse events for each Subject during the course of the study. All AEs will be listed on the adverse event case report forms. All pre-existing medical conditions and baseline dialysis stability signs and symptoms will be recorded on baseline case report forms for medical history and signs and symptoms.

Starting with the first treatment during Treatment period 1 with the Tablo[™] Hemodialysis System, any new event/experience that was not present at baseline, or worsening of an event present at baseline, is considered an adverse event. Recorded Adverse Events will include, but are not limited to:

- infections (other than those defined in the Primary Safety Endpoint),
- hypotension,

Note: Unchanged, chronic conditions are not adverse events and should not be recorded on the adverse event page of the CRF.

Note: Laboratory values that are abnormal will not be considered as adverse events unless medical intervention is required. Clinical laboratory data will be monitored and values that are outside of the normal ranges will be separately summarized by time point for each treatment period (In-Center and In-Home). During the In-Center treatment period, summary statistics (mean, standard deviation, median, range, n) on laboratory values collected will be computed on the raw data. During the In-Home treatment period, summary statistics (mean, standard deviation, median, range, n) on laboratory values collected will be computed on the raw data. During the In-Home treatment period, summary statistics (mean, standard deviation, median, range, n) on laboratory values collected will be created for each laboratory values collected will be computed on the raw data. Individual tables will be created for each laboratory panel and quantitative parameter combination. In addition, a summary table will be created for each laboratory panel (hematology and chemistry) to display the number and percentage of subjects who have results that fall out of the normal ranges for each laboratory parameter by time point for each of Treatment Period 1 and 2.

Adverse events will be monitored until they are adequately resolved or explained. Should an adverse event be ongoing at the end of the Subject's last study treatment the medical care plan for the Subject will be described and documented.

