6 STUDY DESIGN

6.1 Overview

This is a prospective, multicenter, open label, non-randomized, cross-over study. Subjects will be enrolled in the trial for approximately 21 weeks during which time Subjects will use the Tablo[™] Hemodialysis

System for dialysis treatments in all study phases. There are four periods during which the Tablo System will be utilized; run-in, treatment period 1, training/transition and treatment period 2.

• **Run-in** – Subjects will undergo dialysis treatment 4 times/week for 1 week In-Center. Treatments will be administered by study staff.

Confirmation of study eligibility will be assessed after the Subject completes this one-week run-in period.

• Treatment Period 1, In-Center – Subjects will undergo dialysis treatment 4 times/week for 32 treatments (approximately 8 weeks) In-Center. Treatments will be administered by study staff. Subjects are expected to undergo no more than 4 complete treatments per week during this treatment period.

Subjects are considered enrolled in the study if they meet all inclusion and exclusion criteria and have started the first study treatment during the first treatment period.

- In-Home Transition—Subjects will undergo device training for the study, then perform self-care dialysis 4 times/week for approximately 4 weeks. Treatments performed during the first portion will be completed In-Center under supervision. Treatments performed during the second portion will be completed In-Home. This second portion will assess subject stability in a new care environment. Supervision will be at the discretion of the Investigator.
- **Treatment Period 2, In-Home** Subjects will undergo self-care dialysis treatment 4 times/week for 32 treatments (approximately 8 weeks) In-Home. Subjects are expected to undergo no more than 4 complete treatments per week during this treatment period.
- **Follow-**Up---Subjects treatment modality will be followed for up to 5 years post study completion.

Figure 1: Study Design

Data collected during Treatment Period 1 and Treatment Period 2 will be used to assess the primary endpoints.

In the event a subject undergoes more than 4 complete treatments per week, during Treatment Period 1 and Treatment Period 2, the additional treatment(s) will be reported as a protocol deviation per Section 13.3.2.

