8 STUDY PROCEDURES

8.1 Baseline Evaluation

The baseline evaluation will include, but is not limited to, the following testing and assessments, and will be conducted prior to initiating the Run-In period per Appendix B:

- Documentation of consent
- Demographics (Sex, Age, Ethnicity, Race)
- Physical Examination
- Medical History (including history of vascular access)
- Hemodialysis prescription (e.g., equipment, number of times dialyzed per week, and whether inhome or in-clinic settings)
- Laboratory Values
 - Documentation of Laboratory values for 3 months prior to Run-In.
 - Laboratory Testing (hematology and chemistry) as needed*
- Assessment of kinetics
- Routine signs and symptoms
- Concomitant medications

* If the subject has had lab work within two weeks of the run-in period that contains all of the protocol specified tests, a repeat lab draw at baseline is not necessary.

If, after completion and review of the above data, the Subject appears to be a good candidate for study enrollment and is assessed as being able to perform self-care, the Investigator will proceed with the runin period using the Tablo Hemodialysis System.

8.2 1-week Run-in

The 1-week run-in period will include, but is not limited to, the following testing, procedures, and assessment per Appendix B:

- Subject's Dialysis Prescription Settings
- Pre-dialysis vitals, including body weight, temperature, blood pressure, and heart rate (pulse)
- Number of dialysis sessions completed
- Post-Dialysis body weight
- Assessment of Kinetics
- Concomitant Medications
- Assessment of dialysis interval adverse events (if any)
- Final assessment of Subject eligibility

All treatments will be performed using the Tablo[™] Hemodialysis System. Dialysis personnel, trained on the use of the device, will input the dialysis prescription as detailed below:

The dialysis prescription will include:

- Access blood flow (set between 300 and 400 ml/min.)
- Dialysate temperature (between 36 and 39 degrees Celsius adjustable by 0.5 degrees increments)
- Composition of dialysate: potassium (limited to 2 mEq/dL versus 3 mEq/dL), bicarbonate (30 to 40 mEq/L adjustable in 1 mEq/L intervals), sodium concentrations (135-145 mEq/L in 1mEq/liter increments)
- Treatment length in minutes between 160 minutes and 240 minutes
- Blood pressure parameters for ultrafiltration
- Heparin dose and anticoagulation parameters

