11.2 Safety Population

The safety population will consist of all Subjects who are enrolled in the study. All safety analyses will be conducted on the safety population.

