1.2 Study Procedures

Inclusion and exclusion criteria will be assessed prior to initiating the In-Center run-in period. Subjects with a diagnosis of ESRD who meet the inclusion and exclusion criteria will be eligible for participation in this study. The In-Center run-in period will take place for one week from Day -7 to Day -1.

Subjects who continue to meet the inclusion and exclusion criteria will enter the first treatment period, which consists of In-Center dialysis using the Tablo

Hemodialysis System. To be considered *enrolled* in the study, the subject must meet all inclusion and exclusion criteria and have started the first study treatment during treatment period 1. The first treatment period will start on Day 1 and continue until the subject completes 32 treatments (approximately 8 weeks, with 4 treatments/week).

Over the approximate four week In-Home transition period, investigational site personnel confirm the Subject or trained care partner is 1) stable in the new care environment, 2) has been appropriately trained on the set up and use of the Tablo Hemodialysis System, and 3) has satisfactorily completed the items of the patient skills assessment. The Subject or trained care partner will be responsible for device set up and initiating therapy under the supervision of study personnel In-Center during the first portion. The second portion of the transition period In-Home will be supervised at the discretion of the investigator.

Subjects or their trained care partner will administer dialysis therapy at home during treatment period 2 according to the investigator's instruction. This In-Home treatment period lasts a total of 32 treatments (approximately 8 weeks, with 4 treatments/week).

During each of the four periods described above, the following assessments will be performed:

- Every treatment: signs and symptoms, subject evaluation of the device, and adverse events.
- Weekly: concomitant medications and pre and post BUN sample collection,
- Monthly: Starting with the baseline evaluation, chemistry and hematology assessments will be performed approximately every four weeks. For analysis purposes, all laboratory results obtained during the baseline evaluation will be considered as the baseline measurements.

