5.0 Analysis of Safety

5.1 Description of Safety Variables

All study-emergent AEs occurring during the study sessions will be recorded and classified on the basis of the Medical Dictionary for Regulatory Activities (MedDRA[®]) terminology. Study-emergent AEs are those AEs with an onset on or after the date of first study treatment. All analysis tables of AEs will be relative to study-emergent AEs.

The primary safety analysis variable is the mean number of adverse events (AEs) from the pre-specified list observed during a dialysis interval as follows:

- Serious AE (SAE)
- Allergic Reaction
- Blood Loss

- Hemolytic Reaction
- Infection
- Intra-Dialysis Event
- Vascular Access Complication
- Pyrogenic Reaction

A dialysis interval is defined as the start of one dialysis treatment until the start of the next dialysis treatment. A dialysis interval is further divided as follows:

- *Treatment*: An event that occurs during dialysis treatment onset through completion
- *Interdialytic*: An event that occurs from the end of the subject's treatment to beginning of dialysis treatment set-up of the next treatment
- *Pre-Treatment*: An event that occurs during dialysis treatment set-up until the start of treatment

Any event that occurs during any of these time periods is considered within the same dialysis interval.

The secondary safety analysis variables are defined as follows:

- All other study-emergent AEs
- Clinical labs (Hematology, Chemistry, and Kinetics [Pre/Post BUN])

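### Subjects treated on the device who stop in the run-in are in no adverse event table, and the plan conflicts on whether run-in events of later-enrolled subjects count

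*Protocol*

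**What the plan says.** Protocol 6.1 sets out the exposure: "There are four periods during which the Tablo System will be utilized; run-in, treatment period 1, training/transition and treatment period 2". On the run-in week, Protocol 8.2 says "All treatments will be performed using the Tablo" system, and it lists assessment of AEs among the run-in procedures. The AE row of Appendix B marks the run-in week. SAP 1.2 agrees: "During each of the four periods described above, the following assessments will be performed", with AEs listed for every treatment. SAP 1.2 also fixes the timing: "The In-Center run-in period will take place for one week from Day -7 to Day -1".

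The counting rules start later. Protocol 9.2.2 treats new or worsened events as AEs "Starting with the first treatment during Treatment period 1". Protocol 11.2 states: "The safety population will consist of all Subjects who are enrolled in the study". SAP 2.2 repeats this. Enrolled means having started Treatment Period 1 (Protocol 6.1, 7.1 and 11.1; SAP 1.2). SAP Table 1, the disposition table, covers enrolled subjects only.

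Protocol 11.6 and SAP 5.1 use a different start point: "Study-emergent AEs are those AEs with an onset on or after the date of first study treatment". SAP 5.1 limits all AE tables to study-emergent events. Table 16 shows In-Center and In-Home; Tables 17-21 show In-Center, In-Home and Overall.

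**The concern.** The run-in is each subject's first exposure to the device in this study, so it is not an unexposed baseline for safety. The pre-specified list includes dialyzer, allergic and pyrogenic reactions, any of which could occur in that week.

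Eligibility is confirmed after the run-in (Protocol 6.1 and 8.2). Some criteria could be failed because of an event during that week:
- a reaction to dialyzer membrane material (exclusion 16)
- an infection needing antibiotics (exclusion 10)
- a major cardiovascular event (exclusion 6)
- loss of a stable vascular access (inclusion 4)

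In such a case both the event and the subject drop out of the reported safety analysis, and the remaining population may be selected for having tolerated first use. With a target of about 30 evaluable subjects, even one serious event in the run-in would matter to a reader of the safety results.

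**Working it through.** **Who is counted.** The two start points can be set against the population definition.

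| Case | Start at Treatment Period 1 (Protocol 9.2.2) | Start at first Tablo treatment (one reading of Protocol 11.6, SAP 5.1) |
|---|---|---|
| Event in the run-in, subject stops there | In no AE table | In no AE table: not in the safety population |
| Event in the run-in, subject later enrols | In no AE table | Can enter Overall in Tables 17-21; no run-in column |
| Event in the transition | Study-emergent; no column of its own | Same |

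The first row is the same under both readings. The second depends on the phrase *first study treatment*. Protocol 11.1 and SAP 1.2 place that phrase in the first treatment period, and SAP 1.2 numbers the run-in before Day 1, which favours the later start. But both passages add the period as a qualifier, and Protocol 11.6 and SAP 5.1 omit it. The text does not settle the matter.

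**Plan's own figure.** Time in trial is 1 (run-in) + 8 (Period 1) + 4 (transition) + 8 (Period 2) = 21 weeks. This reproduces the stated figure of about 21 weeks, so the plan itself counts the run-in as trial time.

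**Share of exposure.** Planned device treatments per subject (Protocol 6.1, SAP 1.1) are 4 + 32 + 16 + 32 = 84, where the transition is 4 per week × 4 weeks = 16.
- Run-in share of all planned device treatments: 4/84 = 4.8%.
- Run-in share of the first In-Center treatments: 4/(4 + 32) = 4/36 = 11%.
- Transition share: 16/84 = 19.0%.
- Share with no AE column of its own: (4 + 16)/84 = 23.8%.

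**Number of treatments.** The target is 30 evaluable subjects and the cap is 50. Run-in treatments are 30 × 4 = 120 or 50 × 4 = 200. Subjects who stop in the run-in add to this; the documents do not say how many to expect.

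**Possible events.** The documents give no expected run-in event rate. At an assumed 1 pre-specified event per 100 treatments, the run-in would hold 120 × 0.01 = 1.2 to 200 × 0.01 = 2.0 events. Over an assumed range of 0.5 to 2 per 100, this runs from 120 × 0.005 = 0.6 to 200 × 0.02 = 4.0.

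**If the run-in rate were higher.** With a run-in rate k times the Treatment Period 1 rate (k assumed), the rate over the first 36 treatments is (32 + 4k)/36 times the Treatment Period 1 rate: 40/36 = 1.11 for k = 2, 44/36 = 1.22 for k = 3 and 52/36 = 1.44 for k = 5. This shows sensitivity only; nothing in the documents gives k.

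**The case against.** A run-in before endpoint counting is a legitimate design choice, and Protocol 6.1 says plainly that the primary endpoints use Treatment Periods 1 and 2. That stands, and the fix leaves it alone.

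Oversight does not stop in the run-in. Protocol 9.3 requires immediate reporting of SAEs and UADEs with no period limit, Protocol 9.2.4 has the Clinical Events Committee periodically review all AEs, and the general definition in Protocol 9.1.1 has no start date. This also stands: the gap is in the reported analysis.

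A reader might infer that no run-in event can reach any safety table. The documents do not support that for subjects who later enrol, because of the Overall column and the untied wording in Protocol 11.6 and SAP 5.1. A reader might also infer that the post-run-in check is there to remove subjects who did badly. No criterion excludes a subject for a run-in AE as such; the most the text supports is that some criteria may have that effect.

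Nor do the documents say that reactions concentrate at first use. The blood tubing cartridge is new at each treatment, the dialyzer is commercially available, subjects with past membrane reactions are excluded, and water and dialysate are tested at installation. First-use reactions remain possible, but a raised run-in rate is an assumption.

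Finally, 4.8% of planned treatments is a small share. That limits the likely number of events, but the subjects who stop in the run-in are still missing altogether.

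**Conclusion.** The point holds in a limited form. On any reading, a subject who receives device treatment and stops in the run-in is in no analysis population, in no AE table and not in the disposition table. For subjects who enrol, the start of AE counting conflicts between Protocol 9.2.2 and Protocol 11.6/SAP 5.1, and the passages must be reconciled. No AE table separates the run-in or the transition, which together make up 23.8% of planned device treatments.

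The effect on event counts cannot be fixed from the documents. The range of 0.6 to 4.0 pre-specified events rests on an assumed rate and covers only subjects who go on to Treatment Period 1. Selection for tolerance is possible but not shown. The change should be made: it concerns complete reporting of device exposure, and it does not alter the primary safety rates or remove any selection behind them.

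**What to change.** 1. In Protocol 9.2.2 and 11.6 and SAP 5.1, define study-emergent AEs as those with onset on or after the first Tablo treatment, run-in included. The baseline evaluation precedes the run-in (Protocol 8.1), so a reference for new or worsened events already exists.
2. In Protocol 11.2 and SAP 2.2, define the safety population as every subject who started a Tablo treatment. Leave the ITT population as it is.
3. Add Run-in and Transition columns to SAP Tables 17-21. Use as each column's denominator the subjects who started a treatment in that period. These tables now divide every column by the whole safety population, so adding subjects who stopped in the run-in would otherwise dilute the In-Center and In-Home percentages.
4. List the subjects who stopped in the run-in with their events, and add them to Table 1.
5. Keep the primary safety rates in Table 16 on Treatment Periods 1 and 2.

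The cost is a protocol and SAP amendment, with IRB approval where Protocol 14.4 requires it, and extra table columns. Overall AE counts may be slightly higher, and the baseline figures in other safety-population tables would take in the added subjects. The schedule already calls for the run-in AE data, and the SAP already gives Week 1 rows to BUN, alarms and prescription changes (Tables 33, 35 and 41). Sites that applied Protocol 9.2.2 literally may have recorded run-in events incompletely, so this should be checked.

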9.2.3 Determination of the Relationship

Determination of whether there is a reasonable possibility that the investigational device caused or contributed to an AE is to be determined by the Investigator and recorded on the CRFs as **not related**, **related or unknown**. Determination should be based on assessment of temporal relationships, biologic plausibility, association (or lack of association) with underlying disease, and presence (or absence) of a more-likely cause.

Definitions for determination of the relationship include:

Not Related: Exposure to the investigational device has not occurred, or the occurrence of the adverse event is not reasonably related in time, or the adverse event is considered unlikely to be related to the use of the investigational device (biologically implausible).

Related: Exposure to the investigational device and the adverse event are reasonably related in time and the investigational device is more likely than other causes to be responsible for the adverse event, or is the most likely cause of the adverse event.

Unknown: Exposure to the device and the occurrence of adverse event cannot be reasonably determined to be unrelated to the device. If the relationship is identified as unknown it will be treated as related to the investigational device.

If any adverse event is considered related to the use of the investigational device, that event will be followed until resolution or until the Investigator determines the event to be chronic or stable.

